8.2.10.2. Comprehensive Hepatic Evaluation

If a participant develops any 1 of the following laboratory or clinical changes, initiate a comprehensive hepatic evaluation.

Participants with normal or near normal baseline (ALT, AST, or ALP <1.5x ULN)	Participants with elevated baseline (ALT, AST, or ALP ≥1.5x ULN)
ALT or AST ≥5x ULN or	ALT or AST ≥3x baseline or ≥250 U/L (whichever occurs first) or
ALP ≥2.5x ULN or	ALP ≥2.5x baseline or

ALT or AST ≥ 3 x ULN with hepatic signs or symptoms ^a or	ALT or AST ≥ 2 x baseline or ≥ 250 U/L (whichever occurs first) with hepatic signs or symptoms ^a or
ALT or AST ≥ 3 x ULN and TBL ≥ 2 x ULN ^b or INR ≥ 1.5	ALT or AST ≥ 2 x baseline or ≥ 250 U/L (whichever occurs first) and TBL ≥ 2 x ULN ^b or INR ≥ 1.5

a Examples of hepatic signs or symptoms: severe fatigue, nausea, vomiting, right upper quadrant abdominal pain, fever, rash, and/or eosinophilia $>5\%$.

b In participants with Gilbert's syndrome, the threshold for TBL may be higher.

Comprehensive hepatic evaluation should include these actions:

- At a minimum, comprehensive hepatic evaluation should include physical examination and a thorough medical history, as outlined above, as well as tests for PT-INR; tests for viral hepatitis A, B, C, and E; tests for autoimmune hepatitis; and an abdominal imaging study (for example, ultrasound or CT scan).
- Based on the participant's history and initial results, further testing should be considered in consultation with the Lilly-designated medical monitor, including tests for hepatitis D virus, cytomegalovirus, Epstein-Barr virus, acetaminophen levels, acetaminophen protein adducts, urine toxicology screen, Wilson's disease, blood alcohol levels, urinary ethyl glucuronide, and blood phosphatidylethanol.
- Based on the circumstances and the investigator's assessment of the participant's clinical condition, the investigator should consider referring the participant for a hepatologist or gastroenterologist consultation, and additional tests including magnetic resonance cholangiopancreatography, endoscopic retrograde cholangiopancreatography, cardiac echocardiogram, or a liver biopsy.
- Clinical and laboratory monitoring should continue at a frequency of 1 to 3 times weekly until levels normalize or return to approximate baseline values.
- All the medical information and tests results related to the hepatic monitoring and comprehensive hepatic evaluation should be collected and recorded in a hepatic safety CRF.

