7.1.3. Temporary Interruption of Study Intervention

During the treatment period of an ISA, the investigator may interrupt a participant's study intervention, for example, due to an AE or a clinically significant laboratory value. The dates of study intervention interruption and restart must be documented.

Details regarding temporary discontinuation or interruption and re-introduction of study intervention, if applicable, are described in the ISAs.

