8.2.9. Pregnancy Testing**Pregnancy testing at Visit 401**

Serum pregnancy testing will be performed using a central study laboratory during the screening period of this master protocol (Sections [1.3](#) and [10.2](#)).

Pregnancy testing after Visit 401

Urine pregnancy testing after Visit 401 will be performed locally according to the SoA of the relevant ISA if required. If a urine pregnancy test is not available, a serum pregnancy test performed by a local laboratory is an acceptable alternative.

If a urine pregnancy test is inconclusive at any visit, an additional serum pregnancy test should be performed. If the specified visit includes administration of study intervention, the pregnancy test must be “negative” within 24 hours before the study intervention is administered.

Pregnancy testing at any time during the study

Additional pregnancy testing may be performed at any time in the study, at the discretion of the investigator, if the participant’s menstrual period is missed or there is clinical suspicion of pregnancy, or as required by local law or regulation.

Discontinuation of participants who are pregnant

Participants who are pregnant will be permanently discontinued from the study intervention (Section 7.1).

8.2.10. Hepatic Safety Monitoring, Evaluation, and Criteria for Study Drug Interruption or Discontinuation

The following tables summarize actions to take based on abnormal hepatic laboratory or clinical changes.

Participants with normal or near normal baseline (ALT, AST, or ALP <1.5x ULN)

If this laboratory value is observed...	Then...		
	Initiate or continue close hepatic monitoring	Initiate comprehensive evaluation	Interrupt or discontinue study drug
ALT or AST ≥ 3 x ULN	X		
ALP ≥ 2 x ULN	X		
TBL ≥ 2 x ULN ^b	X		
ALT or AST ≥ 5 x ULN	X	X	
ALP ≥ 2.5 x ULN	X	X	
ALT or AST ≥ 3 x ULN with hepatic signs or symptoms ^a	X	X	X
ALT or AST ≥ 5 x ULN for more than 2 weeks	X	X	X
ALT or AST ≥ 8 x ULN	X	X	X
ALT or AST ≥ 3 x ULN and TBL ≥ 2 x ULN ^b or INR ≥ 1.5	X	X	X
ALP ≥ 3 x ULN	X	X	X
ALP ≥ 2.5 x ULN and TBL ≥ 2 x ULN ^b	X	X	X
ALP ≥ 2.5 x ULN with hepatic signs or symptoms ^a	X	X	X

^a Examples of hepatic signs or symptoms: severe fatigue, nausea, vomiting, right upper quadrant abdominal pain, fever, rash, and/or eosinophilia >5%.

^b In participants with Gilbert’s syndrome, the threshold for TBL may be higher.

Participants with elevated baseline (ALT, AST, or ALP ≥ 1.5 x ULN)

If this laboratory value is observed...	Then...		

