	Initiate or continue close hepatic monitoring	Initiate comprehensive evaluation	Interrupt or discontinue study drug
ALT or AST ≥ 2 x baseline	X		
ALP ≥ 2 x baseline	X		
TBL ≥ 2 x ULN ^b	X		
ALT or AST ≥ 3 x baseline or ≥ 250 U/L (whichever occurs first)	X	X	
ALP ≥ 2.5 x baseline	X	X	
ALT or AST ≥ 2 x baseline or ≥ 250 U/L (whichever occurs first) with hepatic signs or symptoms ^a	X	X	X
ALT or AST ≥ 3 x baseline or ≥ 250 U/L (whichever occurs first) for more than 2 weeks	X	X	X
ALT or AST ≥ 4 x baseline or ≥ 400 U/L (whichever occurs first)	X	X	X
ALT or AST ≥ 2 x baseline or ≥ 250 U/L (whichever occurs first) and TBL ≥ 2 x ULN ^b or INR ≥ 1.5	X	X	X
ALP ≥ 3 x baseline	X	X	X
ALP ≥ 2.5 x baseline and TBL ≥ 2 x ULN ^b	X	X	X
ALP ≥ 2.5 x baseline with hepatic signs or symptoms ^a	X	X	X
If this laboratory value is observed...	Then...		
	Initiate or continue close hepatic monitoring	Initiate comprehensive evaluation	Interrupt or discontinue study drug
ALT or AST ≥ 2 x baseline	X		
ALP ≥ 2 x baseline	X		
TBL ≥ 2 x ULN ^b	X		
ALT or AST ≥ 3 x baseline or ≥ 250 U/L (whichever occurs first)	X	X	
ALP ≥ 2.5 x baseline	X	X	
ALT or AST ≥ 2 x baseline or ≥ 250 U/L (whichever occurs first) with hepatic signs or symptoms ^a	X	X	X
ALT or AST ≥ 3 x baseline or ≥ 250 U/L (whichever occurs first) for more than 2 weeks	X	X	X
ALT or AST ≥ 4 x baseline or ≥ 400 U/L (whichever occurs first)	X	X	X
ALT or AST ≥ 2 x baseline or ≥ 250 U/L (whichever occurs first) and TBL ≥ 2 x ULN ^b or INR ≥ 1.5	X	X	X
ALP ≥ 3 x baseline	X	X	X
ALP ≥ 2.5 x baseline and TBL ≥ 2 x ULN ^b	X	X	X
ALP ≥ 2.5 x baseline with hepatic signs or symptoms ^a	X	X	X

^a Examples of hepatic signs or symptoms: severe fatigue, nausea, vomiting, right upper quadrant abdominal pain, fever, rash, and/or eosinophilia >5%.

^b In participants with Gilbert's syndrome, the threshold for TBL may be higher.

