8.2.10.1. Close Hepatic Monitoring

If a participant develops any 1 of these changes, initiate close hepatic monitoring:

Participants with normal or near normal baseline (ALT, AST, or ALP <1.5x ULN)	Participants with elevated baseline (ALT, AST, or ALP ≥1.5x ULN)
ALT or AST ≥3x ULN or	ALT or AST ≥2x baseline
ALP ≥2x ULN or	ALP ≥2x baseline
TBL ≥2x ULN ^a	TBL ≥2x ULN ^a

^a In participants with Gilbert's syndrome, the threshold for TBL may be higher.

Close hepatic monitoring should include these actions:

- Laboratory tests (Section 10.2), including ALT, AST, ALP, TBL, D. Bil, GGT, CK, and CBC with differential, should be checked within 48 to 72 hours of the detection of elevated liver tests to confirm the abnormality and to determine if it is increasing or decreasing.
- If the abnormality persists, clinical and laboratory monitoring should continue at a frequency of 2 to 3 times weekly until levels normalize or return to approximate baseline values.
- In addition to lab tests, basic evaluation for possible causes of abnormal liver tests should be initiated by the investigator in consultation with the Lilly-designated medical monitor. At a minimum, this evaluation should include physical examination and a thorough medical history, including current symptoms, recent illnesses (for example, heart failure, systemic infection, hypotension, or seizures), recent travel, concomitant medications (including over-the-counter), herbal and dietary supplements, history of alcohol drinking and other substance abuse.

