8.2.10.3. Study Drug Interruption or Discontinuation

If a participant develops any 1 of the following laboratory or clinical changes, interrupt the study drug and continue close monitoring and comprehensive hepatic evaluation as described in Sections 8.2.10.1 and 8.2.10.2.

Participants with normal or near normal baseline (ALT, AST, or ALP <1.5x ULN) ALT or AST ≥ 3 x ULN with hepatic signs or symptoms ^a or ALT or AST ≥ 5 x ULN for more than 2 weeks or ALT or AST ≥ 8 x ULN or	Participants with elevated baseline (ALT, AST, or ALP ≥ 1.5x ULN) ALT or AST ≥ 2 x baseline or ≥ 250 U/L (whichever occurs first) with hepatic signs or symptoms ^a or ALT or AST ≥ 3 x baseline or ≥ 250 U/L (whichever occurs first) for more than 2 weeks or ALT or AST ≥ 4 x baseline or ≥ 400 U/L (whichever occurs first) or
---	---

ALT or AST ≥ 3 x ULN and TBL ≥ 2 x ULN^b or
 INR ≥ 1.5 **or**
 ALP ≥ 3 x ULN **or**
 ALP ≥ 2.5 x ULN and TBL ≥ 2 x ULN^b **or**
 ALP ≥ 2.5 x ULN with hepatic signs or
 symptoms^a

ALT or AST ≥ 2 x baseline or ≥ 250 U/L
 (whichever occurs first) and TBL ≥ 2 x ULN^b or INR ≥ 1.5 **or**
 ALP ≥ 3 x baseline **or**
 ALP ≥ 2.5 x baseline and TBL ≥ 2 x ULN^b **or**
 ALP ≥ 2.5 x baseline with hepatic signs or symptoms^a

^a Examples of hepatic signs or symptoms: severe fatigue, nausea, vomiting, right upper quadrant abdominal pain, fever, rash, and/or eosinophilia $>5\%$.

^b In participants with Gilbert's syndrome, the threshold for TBL may be higher.

Interruption or discontinuation of study drug should include these actions:

- While the participant is not receiving the study drug, clinical and laboratory monitoring should continue at a frequency of 1 to 3 times weekly until liver tests normalize or return to approximate baseline values.
- If the hepatic event continues past the anticipated end of the study (that is, data lock) the investigator should consult with the Lilly-designated medical monitor to determine the need for further data collection beyond the end date of the study (that is, data lock date).
- All the medical information and tests results related to the close hepatic monitoring and comprehensive hepatic evaluation should be collected and recorded in a hepatic safety CRF.

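### Section 8.2.10.2 allows once-weekly liver monitoring at a more severe trigger while dosing may continue; Section 8.2.10.1, which covers the same participants, asks for at least twice weekly

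*Protocol*

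**What the plan says.** Three adjacent subsections of the Protocol each give a monitoring frequency.

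- **Section 8.2.10.1 (close monitoring).** After a recheck at 48 to 72 hours: "If the abnormality persists, clinical and laboratory monitoring should continue at a frequency of 2 to 3 times weekly", until values normalise or come back near baseline. The panel is named, "including ALT, AST, ALP, TBL, D. Bil, GGT, CK, and CBC with differential".
- **Section 8.2.10.2 (comprehensive evaluation).** "Clinical and laboratory monitoring should continue at a frequency of 1 to 3 times weekly until levels normalize or return to approximate baseline values". No condition about being on or off study drug is attached.
- **Section 8.2.10.3 (interruption or discontinuation).** "While the participant is not receiving the study drug, clinical and laboratory monitoring should continue at a frequency of 1 to 3 times weekly". Here the lower floor is expressly tied to being off drug.

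The action tables in Section 8.2.10 have three columns. The first, "Initiate or continue close hepatic monitoring", is marked on every row. Some rows, such as "ALT or AST ≥ 5 x ULN", are marked for close monitoring and comprehensive evaluation but not for interruption.

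**The concern.** A participant at one of those rows falls under 8.2.10.1 and 8.2.10.2 together and may still be taking study drug. The floor is two checks a week at the milder tier (ALT or AST at least 3x ULN) and one a week in the section written for the more severe tier (at least 5x ULN). A lower floor makes sense once exposure has stopped, and that is how 8.2.10.3 uses it. Section 8.2.10.2 gives no reason for it while exposure may continue.

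These participants are one step below mandatory interruption. Several stopping thresholds are read from the routine liver panel: ALT or AST at least 8x ULN (with elevated baseline, at least 4x baseline or 400 U/L), added bilirubin elevation, and ALP at least 3x. A site working from the 8.2.10.2 list alone could check once weekly and see such a crossing some days later than 8.2.10.1 intends.

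**Working it through.** **Step 1. Which triggers are affected.** Section 8.2.10.2 lists four triggers in each of two baseline columns, so 4 x 2 = 8. Against the action tables:

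| Trigger in 8.2.10.2 | Close monitoring | Comprehensive evaluation | Interrupt drug |
|---|---|---|---|
| Normal baseline: ALT/AST ≥5x ULN | yes | yes | no |
| Normal baseline: ALP ≥2.5x ULN | yes | yes | no |
| Normal baseline: ALT/AST ≥3x ULN with symptoms | yes | yes | yes |
| Normal baseline: ALT/AST ≥3x ULN with TBL ≥2x ULN or INR ≥1.5 | yes | yes | yes |
| Elevated baseline: ALT/AST ≥3x baseline or ≥250 U/L | yes | yes | no |
| Elevated baseline: ALP ≥2.5x baseline | yes | yes | no |
| Elevated baseline: ALT/AST ≥2x baseline or ≥250 U/L with symptoms | yes | yes | yes |
| Elevated baseline: ALT/AST ≥2x baseline or ≥250 U/L with TBL ≥2x ULN or INR ≥1.5 | yes | yes | yes |

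Two per column, 4 of 8, carry no interruption mark. The other four require interruption and are outside this point.

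**Step 2. Does the text settle which frequency applies?** Section 8.2.10.2 refers back once: "comprehensive hepatic evaluation should include physical examination and a thorough medical history, as outlined above". That covers examination and history only. It then states its own frequency, with no precedence sentence.

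**Step 3. Minimum checks in 14 days.** Under 8.2.10.2: 1 x 2 = 2. Under 8.2.10.1: 2 x 2 = 4.

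**Step 4. Longest gap and mean wait.** The Protocol does not fix spacing within a week. Assume a weekly pattern that repeats. For a threshold crossed at a uniformly random time (a second assumption), the mean wait to the next check is sum(gap²) / (2 x 7).

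| Pattern | Gaps (days) | Longest gap | Shorter than once weekly by | Mean wait | Mean extra delay if once weekly |
|---|---|---|---|---|---|
| Once weekly | 7 | 7 | – | 49/14 = 3.50 | – |
| Twice weekly, even | 3.5, 3.5 | 3.5 | 3.5 | 24.5/14 = 1.75 | 1.75 |
| Twice weekly | 3, 4 | 4 | 3 | 25/14 = 1.79 | 1.71 |
| Twice weekly | 2, 5 | 5 | 2 | 29/14 = 2.07 | 1.43 |
| Twice weekly, consecutive days | 1, 6 | 6 | 1 | 37/14 = 2.64 | 0.86 |

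The longest gap differs by 1 to 3.5 days and the mean extra delay is about 0.9 to 1.75 days. This describes continuing monitoring after the 48 to 72 hour recheck. No delay is claimed for INR, which is not in the 8.2.10.1 panel, or for the triggers based on symptoms or on more than 2 weeks' duration.

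**The case against.** The strongest reply is that the two instructions are compatible: checking 2 to 3 times weekly meets both. The tables keep close monitoring in force on every row, and most participants at the four triggers also meet the entry thresholds of 8.2.10.1 (5x ULN exceeds 3x ULN; 3x baseline exceeds 2x baseline). Section 8.2.10.2 cannot run on its own either: it tells sites to continue monitoring, which implies monitoring already under way, and it names no routine liver panel. Both bullets say should rather than must. Other safeguards exist: the early recheck, consultation with the sponsor's medical monitor, and the investigator's freedom under Section 7.1.3 to interrupt drug, "for example, due to an AE or a clinically significant laboratory value".

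Most of this stands. A careful site would monitor 2 to 3 times weekly, and the delay figures apply only to a site working at the bare minimum of 8.2.10.2. How often that would happen cannot be estimated from the Protocol. But if 8.2.10.1 is meant to govern, the lower figure in 8.2.10.2 has no function for someone still dosing with a persisting abnormality. If it is not, the worse tier has the looser rule. The section specific to these participants states the looser number, and the safeguards do not correct it.

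**Conclusion.** The point holds as a minor safety-wording error. For 4 of the 8 triggers in 8.2.10.2, the stated floor is one check a week where 8.2.10.1 sets two, with dosing not required to stop. The 2-against-4 count over 14 days follows directly from the text, given an abnormality that persists on recheck. The day figures rest on the repeating weekly pattern and, for the mean delay, on random timing of the crossing; they should be read as illustrations for a site at the minimum. These safety sections apply to all ISAs, so the ambiguity carries into any ISA that does not set its own rule.

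**What to change.** In Section 8.2.10.2, either raise the lower bound to two checks weekly for participants still receiving study drug, or add one sentence stating that the 8.2.10.1 frequency applies while dosing continues. Leave 8.2.10.3 as it is, since its once-weekly floor is already limited to participants off drug.

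The cost is one number or one sentence. At the minimum frequencies it means at most 4 − 2 = 2 more checks per 14 days for participants at these triggers, which 8.2.10.1 already asks for. No endpoint, power or error rate changes.

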8.2.10.3. Study Drug Interruption or Discontinuation

If a participant develops any 1 of the following laboratory or clinical changes, interrupt the study drug and continue close monitoring and comprehensive hepatic evaluation as described in Sections 8.2.10.1 and 8.2.10.2.

Participants with normal or near normal baseline (ALT, AST, or ALP <1.5x ULN) ALT or AST ≥ 3 x ULN with hepatic signs or symptoms ^a or ALT or AST ≥ 5 x ULN for more than 2 weeks or ALT or AST ≥ 8 x ULN or	Participants with elevated baseline (ALT, AST, or ALP ≥ 1.5x ULN) ALT or AST ≥ 2 x baseline or ≥ 250 U/L (whichever occurs first) with hepatic signs or symptoms ^a or ALT or AST ≥ 3 x baseline or ≥ 250 U/L (whichever occurs first) for more than 2 weeks or ALT or AST ≥ 4 x baseline or ≥ 400 U/L (whichever occurs first) or
---	---

ALT or AST ≥ 3 x ULN and TBL ≥ 2 x ULN^b or
 INR ≥ 1.5 **or**
 ALP ≥ 3 x ULN **or**
 ALP ≥ 2.5 x ULN and TBL ≥ 2 x ULN^b **or**
 ALP ≥ 2.5 x ULN with hepatic signs or
 symptoms^a

ALT or AST ≥ 2 x baseline or ≥ 250 U/L
 (whichever occurs first) and TBL ≥ 2 x ULN^b or INR ≥ 1.5 **or**
 ALP ≥ 3 x baseline **or**
 ALP ≥ 2.5 x baseline and TBL ≥ 2 x ULN^b **or**
 ALP ≥ 2.5 x baseline with hepatic signs or symptoms^a

^a Examples of hepatic signs or symptoms: severe fatigue, nausea, vomiting, right upper quadrant abdominal pain, fever, rash, and/or eosinophilia $>5\%$.

^b In participants with Gilbert's syndrome, the threshold for TBL may be higher.

Interruption or discontinuation of study drug should include these actions:

- While the participant is not receiving the study drug, clinical and laboratory monitoring should continue at a frequency of 1 to 3 times weekly until liver tests normalize or return to approximate baseline values.
- If the hepatic event continues past the anticipated end of the study (that is, data lock) the investigator should consult with the Lilly-designated medical monitor to determine the need for further data collection beyond the end date of the study (that is, data lock date).
- All the medical information and tests results related to the close hepatic monitoring and comprehensive hepatic evaluation should be collected and recorded in a hepatic safety CRF.
- Resumption of the study drug after interruption for a hepatic reason can be considered only in consultation with the Lilly designated medical monitor and only if the liver test results returned to near baseline and if a self-limited, non-study drug etiology is identified. Otherwise, the study drug should be permanently discontinued.

8.2.11. Hepatitis B and Hepatitis C Testing and Monitoring

Hepatitis B testing

As specified in the SoA (Section 1.3), initial testing for HBV infection includes HbsAg and hepatitis B core antibody (HbcAb).

- If HbsAg is negative and HbcAb is negative, the participant is not excluded.
- If HbsAg is positive, the participant is excluded.
- If HbsAg is negative and HbcAb is positive, further testing for HBV DNA is required.
 - If the screening HBV DNA is positive, the participant is excluded.

If screening HBV DNA is negative, the participant is not excluded. Repeat testing for HBV DNA is required at least every 3 months during the study.

Hepatitis C testing

As specified in the SoA (Section 1.3), initial testing for HCV infection includes testing for anti-HCV.

- If anti-HCV is positive, a test for circulating HCV RNA is required.
- If HCV RNA test is negative, the participant is not excluded.
- If HCV RNA test is positive, the participant is excluded (see Section 5.2).

Participants who have had HCV infection and have been successfully treated, defined as a sustained virologic response (HCV RNA by PCR negative for at least 24 weeks following treatment completion), are not excluded on the basis of HCV as long as HCV RNA test is negative at screening.

8.2.12. Mood Changes, Suicidal Ideation, and Suicidal Behavior Risk Monitoring

Participants who have obesity or are overweight are at increased risk for depression (Luppino et al. 2010). Depression can increase the risk for suicidal ideation and behavior. Therefore, study participants will be screened at trial entry and monitored during the study for depression, suicidal ideation, and suicidal behavior.

Participants should be monitored appropriately and observed closely for suicidal ideation and behavior or any other unusual changes in behavior, especially at the beginning and end of the course of treatment, or at the time of dose changes, either increases or decreases. Consideration should be given to discontinuing the study medication in who experience signs of suicidal ideation or behavior, following a risk assessment.

Baseline and treatment-emergent assessment of depression, suicidal ideation, and suicidal behavior will be monitored during the study using the C-SSRS and PHQ-9. Scores of the questionnaires must be reviewed by the investigator at the time of each visit, and appropriate actions as described below should be taken.

8.2.12.1. C-SSRS

Columbia Suicide-Severity Rating Scale (C-SSRS) is a scale that captures the occurrence, severity, and frequency of suicidal ideation and behavior during the assessment period via a questionnaire. The scale was developed by the National Institute of Mental Health trial group (TASA) for the purpose of being counterpart to the Columbia Classification Algorithm of Suicide Assessment categorization of suicidal events.

For this study, the C-SSRS is adapted for the assessment of the ideation and behavior categories only. The Intensity of Ideation and Lethality of Behavior sections are removed.

See Section 8.3.1.1 for the collection of the C-SSRS relative to nonleading (spontaneous) AE collection.

